# Nicotine Replacement Therapy

All participants will receive nicotine replacement therapy in session 6, and will be asked to begin using NRT on their quit date (just prior to session 7). Participants will be provided with detailed information and education regarding the use of the nicotine skin patches. This educational component will include a rationale for using the patches, proper placement of the patch, when to use them, possible side effects, and how to report side effects to research staff as they may occur in the course of the study. All participants will also be given the option of one NRT rescue method of their choosing (nicotine gum, lozenges or inhalers).

Medications will be distributed under the consultation of study physician, [name]., Ph.D. [name] prescribes smoking cessation pharmacotherapy for the Durham VA specialty smoking cessation clinic. [name] is familiar with standard smoking cessation pharmacotherapy and side effects. He will determine initial nicotine dosage levels and consult on any adjustments to medication dosage. For example, patients only smoking 10 cigarettes a day would likely not benefit from 21mg/day nicotine patches, and will begin NRT at 14mg/day. Recent research has suggested that for heavy smokers (i.e., smokers with CO readings higher than 30 ppm), smoking cessation efficacy is greater when high dose (42 mg) nicotine patches are used in the pre-cessation phase (Rose, personal communication; Rose, 2010). The side effect profile for heavy smokers using a 42 mg patch is low. Rose (personal communication) reports that 2.5% of heavy smokers using a 42 mg. patch pre-quit report vomiting (as compared to 0.4% with the 21 mg. patch). No other adverse effects were reported. Smokers in this study were allowed to use their usual brand of cigarettes. Taken together, these studies suggest that pretreatment with nicotine patch while smoking cigarettes is safe and tolerable.

Heavy smokers (as defined by CO readings greater than 30 ppm) will be prescribed 42 mg. patches. Two weeks after their quit date, participants will lower the dose of the prescribed nicotine patch (i.e., participants receiving 21 mg initially will lower to 14 mg, and those receiving 42 mg will lower to 21 mg). At three weeks after the quit date, any participant who initially received the 42 mg patch will lower the patch dose further to 14 mg. At four weeks post-quit, all participants will replace the 14 mg patch with a 7 mg patch, to be worn for two weeks. All NRT, including both the patch and rescue method, will end 6 weeks after the target quit-smoking date. If any participant has been unable to maintain abstinence during the follow-up period, he/she may be allowed to reinitiate NRT during the follow-up period in order to make a renewed quit attempt. Dosage of NRT will be decided by the study physician at this time point, and will depend upon the participant's most recent smoking patterns and CO reading.

**Table 2. Study Tasks and Procedures** 

Session	Tasks		Payment
	CPT-C + Smoking Intervention	Smoking Intervention	
Phone	

Phone screen

Scheduling screening sess

	Phone screen Scheduling screening session	
1			
2	
 
CPT + smoking treatment 1
 
Questionnaires
 
Introduction to smokefree VET
 
Review EMA practice and begin EMA data collection
 
	
 
Smoking treatment 1
 
Questionnaires
 
Intro to smokefree VET
 
Review EMA practice and begin EMA data collection
 
	\$20 visit
3	
 
2 hr, 15 min
 
CPT + smoking treatment 2
 
Questionnaires
 
	

55 min

Smoking treatment 2

Questionnaires

	\$20 visit; \$25 for EMA; \$25 incentive pay
	1 hr, 45 min	55 min	
4	

CPT + smoking treatment 3

Questionnaires

	

Smoking treatment 3

Questionnaires

	\$20 visit
	1 hr, 45 min	55 min	

Session	Tasks		Payment
5	

CPT + smoking treatment 4

Questionnaires

	

Smoking treatment 4

Questionnaires

	\$20 visit
	1 hr, 45 min	55 min	
6	
 
CPT + smoking treatment 5
 
Questionnaires
 
Receive NRT + rescue method; instructed not to use until quit date
 
Begin bupropion
 
1 hr, 45 min
 
	
 
Smoking treatment 5
 
Questionnaires
 
Receive NRT + rescue method; instructed not to use until quit date
 
Begin bupropion
 
	\$20 visit
7	
 
CPT + smoking treatment 6
 
Questionnaires
 
QUIT DATE/Relapse Prevention
 
Begin patch NRT + rescue method
 
EMA data collection
 
	
 
Smoking treatment 6
 
Questionnaires
 
QUIT DATE/Relapse         Prevention     
 
Begin patch NRT + rescue         method     
 
EMA data collection
 
	\$20 visit
	1 hr, 45 min	55 min	
8	
 
CPT 7 + Relapse         Prevention/Renewed         Quit Attempt
 
Verify Smoking         Abstinence
 
Questionnaires
 
Continue 21 or 42 mg         patch NRT + rescue         method
 
	
 
Smoking treatment 7
 
Verify Smoking Abstinence
 
Questionnaires
 
Continue 21 or 42 mg patch NRT + rescue method
 
	\$20 visit; \$25 for EMA; \$25 incentive pay
	1 hr, 45 min	55 min	
9	
 
CPT 8 + Relapse         Prevention/Renewed         Quit Attempt
 
Verify Smoking         Abstinence
 
Questionnaires
 
Step down to 21 or 14         mg patch NRT + rescue         method
 
	
 
Smoking treatment 8
 
Verify Smoking Abstinence
 
Questionnaires
 
Step down to 21 or 14 mg patch NRT + rescue method
 
	\$20 visit

Session	Tasks		Payment
	1 hr, 45 min	55 min	
10	
 
CPT 9 Relapse         Prevention/Renewed         Quit Attempt
 
Verify Smoking         Abstinence
 
Questionnaires
 
Continue or step down         to 14 mg patch NRT +         rescue method     
 
1 hr, 45 min
 
	
 
Smoking treatment 9
 
Verify Smoking Abstinence
 
Questionnaires
 
Step down to 21 or 14 mg patch NRT + rescue method
 
	\$20 visit
11	
 
CPT 10 + Relapse         Prevention/Renewed         Quit Attempt
 
Verify Smoking         Abstinence
 
Questionnaires
 
Step down to 7mg patch         NRT + rescue method
 
	
 
Smoking treatment 10
 
Verify Smoking Abstinence
 
Questionnaires
 
Step down to 7mg patch NRT + rescue method
 
	\$20 visit
	1 hr, 45 min	55 min	
12	
 
CPT 11 + Relapse         Prevention/Renewed         Quit Attempt
 
Verify Smoking         Abstinence
 
Questionnaires
 
Continue 7mg patch         NRT + rescue method
 
	
 
Smoking treatment 11
 
Verify Smoking Abstinence
 
Questionnaires
 
Continue 7mg patch NRT + rescue method
 
	\$20 visit
13	
 
1 hr, 45 min
 
CPT 12 + Relapse         Prevention/Renewed         Quit Attempt
 
Verify Smoking         Abstinence
 
Questionnaires
 
End of NRT
 
Continue bupropion
 
Weight measurement
 
Begin 1 week of EMA
 
	
 
Smoking treatment 12
 
Verify Smoking Abstinence
 
Questionnaires
 
End of NRT
 
Continue bupropion
 
Weight measurement
 
Begin 1 week of EMA data collection
 
	\$20 visit

Session	Tasks		Payment
	data collection		
	1 hr, 15 min	30 min	
14	
 
End EMA data collection; Return study equipment
 
Verify Smoking Abstinence
 
CAPS
 
		\$20 visit; \$25 for EMA; \$25 incentive pay; \$35 equipment return
	60 min		
15 (6 mos.	
 
Verify Smoking Abstinence
 
If Not Abstinent, Timeline Follow Back
 
Questionnaires
 
		\$50 visit
quit	End bupropion		
date)	

Weight measurement

CAPS

		
	60 min		
16-27	Not applicable	CPT-C (if desired), at 60 minutes per session over three months	None
Total			\$545

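### The nicotine-patch taper is internally inconsistent: the two columns of Table 2 differ at session 10, and a 14 mg starter has no sequence that fits both the text and the table

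*Combined protocol and SAP*

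**What the plan says.** The taper is described twice in the combined protocol and SAP.

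**Nicotine Replacement Therapy section.** The study physician sets the starting patch: "He will determine initial nicotine dosage levels and consult on any adjustments to medication dosage". As an example, "patients only smoking 10 cigarettes a day would likely not benefit from 21mg/day nicotine patches, and will begin NRT at 14mg/day". Smokers with CO readings above 30 ppm start on 42 mg. Then:

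- Week 2: "Two weeks after their quit date, participants will lower the dose of the prescribed nicotine patch". Steps are given from 21 to 14 mg and from 42 to 21 mg only.
- Week 3: "any participant who initially received the 42 mg patch will lower the patch dose further to 14 mg".
- Week 4: everyone exchanges a 14 mg patch for a 7 mg patch, worn for two weeks.
- Week 6: all NRT ends.

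None of these steps depends on arm.

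**Table 2.** Session 7 is the quit date.

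- Session 8, both columns: "Continue 21 or 42 mg patch NRT + rescue method".
- Session 9, both columns: step down to 21 or 14 mg.
- Session 10, CPT-C column: "Continue or step down" to 14 mg.
- Session 10, smoking-only column: "Step down to 21 or 14 mg patch NRT + rescue method", the same words as its session 9 cell.
- Session 11, both columns: step down to 7 mg.
- Session 13, both columns: NRT ends.

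The Objectives describe the comparator as receiving the same smoking treatment without CPT-C. The eligibility list sets the smoking floor at ten cigarettes a day.

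**The concern.** Table 2 is the visit-by-visit schedule that staff are likely to work from. At one visit its two columns carry different patch instructions, and only the CPT-C entry agrees with the text. The comparison is meant to isolate CPT-C on a common background of smoking treatment, and the analysis for Hypothesis 3 regresses Week-6 abstinence on group. A written difference in nicotine dosing between arms is therefore undesirable even if it is small.

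The second problem concerns the lightest eligible smokers. The example of a 14 mg start describes someone exactly at the entry floor, so such participants are foreseeable. The taper is written as if everyone started on 21 or 42 mg. Staff would have to improvise for this group and might not do so alike in the two arms.

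**Working it through.** **Aligning sessions with weeks.** The documents do not state that visits after the quit date are weekly. I infer it: with session 7 as week 0, weekly visits put sessions 9, 11 and 13 at weeks 2, 4 and 6. Table 2 has its first step-down, the 7 mg step and the end of NRT at those sessions, which agrees with the text. Session 10 is then week 3.

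**Reproducing the stated duration.** The text gives NRT for 6 weeks.

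- 42 mg starters: 2 + 1 + 1 + 2 = 6 weeks.
- 21 mg starters: 2 + 2 + 2 = 6 weeks.
- Table 2: session 13 − session 7 = 6 weekly intervals.

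For these two groups the text is complete and agrees with the table's length.

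**Sequence given by the text (mg/day in each week after the quit date).**

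| Start | Weeks 1–2 | Week 3 (from session 9) | Week 4 (from session 10) | Weeks 5–6 |
|---|---|---|---|---|
| 42 mg | 42 | 21 | 14 | 7 |
| 21 mg | 21 | 14 | 14 | 7 |

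Both rows fit every cell of the CPT-C column.

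**Session 10, smoking-only column.**

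- A 21 mg starter has worn 14 mg since session 9. Neither 21 nor 14 mg is a step down from 14 mg, so the instruction cannot be carried out as worded.
- A 42 mg starter has worn 21 mg since session 9. Of the two listed doses only 14 mg is a step down, yet 21 mg is also listed.

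**Size if the cell were read as staying on 21 mg.** For a 42 mg starter:

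- Text: 42×2 + 21 + 14 + 7×2 = 133 mg-weeks (133 × 7 = 931 mg nominal).
- Alternative: 42×2 + 21 + 21 + 7×2 = 140 mg-weeks (140 × 7 = 980 mg).
- Difference: 7 mg/day × 7 days = 49 mg; 140/133 = 1.05.
- Within the affected week: 21/14 = 1.5.

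That reading would also take the participant from 21 to 7 mg at session 11, whereas the four-week sentence presumes a 14 mg patch is being worn.

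**14 mg starters.** Two readings, used only to test consistency:

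| Reading | Two-week sentence (lower the dose) | Four-week sentence (exchange a 14 mg patch) | Session 8 | Session 9 |
|---|---|---|---|---|
| Stay on 14 mg to week 4 | Not met | Met | No entry for 14 mg | 14 mg is listed, but is not a step down |
| Lower at week 2 | Met | Not met | No entry for 14 mg | No fitting entry |

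No reading satisfies both sentences, and neither fits sessions 8 and 9. Staying on 14 mg does fit the CPT-C cell at session 10 and both columns from session 11.

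**The case against.** The strongest reply is that these are drafting slips with little practical effect. Much of it stands.

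- A reader might infer that Table 2 makes heavy smokers in the smoking-only arm wear a higher dose than those in the CPT-C arm. The documents do not support that. The cell says to step down, and from 21 mg the only listed step down is 14 mg, which matches the other column and the text. The repeated wording looks like an uncorrected copy of session 9. The 5% figure is therefore conditional on one reading.
- A reader might infer that session 8 raises a 14 mg starter to 21 mg or more. It does not: the verb is continue, so the cell leaves this group out.
- The 14 mg start is given as an example, and the study physician sets initial doses and consults on adjustments. Part of the second problem is thus an unspecified path under medical oversight.
- A reader might call this a safety problem or a bias in the Week-6 outcome. The documents do not establish either. The Nicotine toxicity section reports no serious toxicity at patch doses up to 44 mg/24 hours. Week-6 is not defined, but if it means six weeks after the quit date, both columns give 7 mg for the two weeks before it.
- The Intervention Protocol lets the quit date move earlier with medications moved to match, so the link between session and dose is only nominal.

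The contradictions remain all the same. Physician oversight does not reconcile two written schedules. The text leaves the dose expressly to the physician only for the initial dose and when NRT is restarted in follow-up; for adjustments it has him consult.

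**Conclusion.** The point holds as an internal inconsistency in an operative schedule, in two parts. First, the smoking-only cell at session 10 disagrees with the CPT-C cell and with the three-week rule; it cannot be carried out as worded for 21 mg starters and is ambiguous for 42 mg starters. Second, 14 mg starters face two sentences that cannot both be met and have no fitting entry at sessions 8 and 9.

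The conditional size of the first part is 7 mg-weeks in 133, about 5% of nominal patch exposure, confined to one week and to 42 mg starters. This rests on weekly visits after the quit date and on reading the cell as no change. The share of participants starting on 42 or 14 mg is not given, so a trial-level effect cannot be calculated. Any effect on abstinence or safety is probably small. Sample size, power and error rate are not affected. It is still worth correcting, because the design depends on both arms receiving the same smoking treatment.

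**What to change.** The sponsor and study physician should reconcile the Nicotine Replacement Therapy section with Table 2, sessions 8 to 11. Each starting dose in use, including 14 mg if it is retained, should have one stated sequence from quit date to end of NRT, tied to weeks since the quit date and printed identically in both columns. Which doses those are is for them to decide; no view is offered here.

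The cost is an amendment to one section and a few table cells. Participants already treated need no new data collection for this purpose. If dispensed patch strengths are on record, a tabulation by arm at session 10 and for 14 mg starters would show whether the wording had any effect in practice.

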## **Objectives:**

The primary aim of the proposed study is to evaluate the integration of CPT-C and smoking cessation treatment in an individual 12-session PTSD protocol as compared to a protocol including the same smoking cessation treatment for individuals with PTSD, but without CPT-C. This intervention will be evaluated with the following hypotheses:

- Compared to the smoking cessation alone protocol, the smoking cessation + concurrent CPT-C protocol will result in reduced frequency and intensity of PTSD symptoms.
- 2) Compared to the smoking cessation alone protocol, the smoking cessation + concurrent CPT-C protocol will result in reduced depressive symptoms.
- 3) The smoking cessation + concurrent CPT-C protocol will result in decreased smoking rates, relative to published data on VA smoking cessation usual care.
- 4) Greater PTSD symptom reduction during the smoking cessation + concurrent CPT-C treatment will result in longer duration to smoking lapse and relapse.
- 5) Exploratory research question: Will use of automated text messaging as an adjunct to smoking cessation be feasible, and will it impact quit rates?

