### **Ecological Momentary Assessment**

Participants will monitor smoking for a total of three weeks: the first week of treatment, the first week of the quit attempt, and the first week following the end of treatment. Participants will be paid \$25 per week for monitoring. Participants will also have the opportunity to earn an extra \$25 per week in incentive pay for returning fully completed electronic diaries. During the monitoring period, participants will record any smoking lapses on the electronic diary (ED), immediately after smoking. Smoking lapse assessments will be accompanied by a "situational assessment" including situation,

activity, smoking craving, mood, and PTSD symptoms. In addition, participants will complete situational assessments on at least five occasions per day selected at random by the ED. Random occasion assessments will be stratified every 2.5 hours. The timing of these assessments will be random with the constraint that no prompts will be given for 10 minutes after a cigarette entry.

Prompting will cover all waking hours. When the diary is not completed, up to 3 reminder signals will be emitted at 1-minute intervals and then the diary program will become inaccessible until the next scheduled occurrence. Smokers will be instructed to stop what they are doing when they hear the signal or plan to smoke a cigarette and complete a diary record, which will take about 1 minute. They will be told to ignore any signal that occurs during an incompatible activity (e.g., driving). To increase adherence, participants will be allowed to suspend prompting when responding would be too costly (e.g., church, driving). In previous research using similar methodology, participants suspended prompting only 2 times per week. Additionally, participants will be able to delay an assessment with a 5-minute delay function. Daily start and stop times will be programmed individually according to each participant's usual sleep pattern and entries will be time-stamped.

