### Assessments After Screening

Prior to each session, participants will complete questionnaires to assess psychiatric symptoms and smoking variables. These include the PTSD checklist (PCL), questions about smoking behavior in the past week, and the Beck Depression Inventory (BDI-II). In the final two sessions, participants will also complete the ASI, QOLI, TRGI, PSQI-A, CAPS, treatment satisfaction, Cook Medley Hostility Scale, e-cigarette use measure, and a question about current non-study psychotherapy. In session 8, participants will complete measures of treatment credibility and expectancy using the Reaction to Treatment Questionnaire (Borkovec & Nau, 1972). At the beginning and end of treatment, therapists will rate their level of allegiance to the therapy they are using with a single question asking "Which treatment do you think leads to better outcomes?" In the final treatment session, participants will also complete measures of SmokeFreeVet usability, and the nicotine dependence stages of change measure. In session 14 (after the final treatment session), participants will be interviewed with the CAPS.

Abstinence and relapse will be monitored by ED entries and at visits 7-14. Participants will provide breath samples for carbon monoxide (CO) analysis at every laboratory visit following their quit date. The first verification of smoking abstinence will occur on the morning following their quit date. Smoking abstinence will be obtained by self-report and verified by comparing CO levels to the level obtained at the baseline visit. The chart below lists the sliding scale of CO values that will be considered validating. At the six month follow-up visit, salivary cotinine will also be used to confirm self-reported

smoking abstinence. The formula in Table 1 below uses the participant's CO reading at the screening visit to determine the threshold that will be considered as confirming smoking abstinence after the quit date for each participant.

Table 1. Carbon Monoxide Thresholds for Validating Smoking Abstinence			
CO SCREENING	AM CO LIMIT		
		AM CO Limit after Overnight	
14-15	15	Abstinence	
16-18	16	AM CO Limit Formula: [14 + (.25 *	
19-21	17	(1.33 * (SCREENCO -14)))]	
22-24	18		
25-27	19		
28-30	20		
31-33	21		
34-36	22		
37-39	23		
40-42	24		
43-45	25		
46-48	26		
49-51	27		
52-54	28		
55-57	29		
58-60	30		
61-63	31		
64-66	32		
67	33		

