## Relapse

All participants will complete the intervention protocol, regardless of smoking relapse. Participants who relapse will have the option of completing the intervention so they can continue to apply smoking cessation skills to subsequent quit attempts. Once the intervention and smoking protocol is completed, participants who relapse will be encouraged to make additional quit attempts until the end of the study at the 6-month follow-up appointment. Relapse will be defined as smoking at least 5 cigarettes a day for 3 consecutive days.

In the follow-up session, if a participant reports an inability to attain or maintain abstinence, we will utilize the Timeline Followback (TLFB) method, which was designed by National Institute on Alcohol Abuse and Alcoholism (NIAAA) to retrospectively evaluate substance use. In this interview, which will last approximately 15 minutes, participants will provide retrospective estimates of their smoking behavior over the time period since their participation. This information will be used to evaluate smoking rates post-quit and relapse incidence among the sample.

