Hypothesis 3. The CPT-C and smoking cessation protocol will result in decreased smoking rates, relative to published data on VA smoking cessation usual care. An outcome variable denoting the proportion of subjects abstinent at Week-6 will be regressed on the group proxy and included covariates using standard logistic regression procedures. A secondary analysis will explore cessation rates at the 6-month follow-up.

Hypothesis 4.-The level of PTSD symptom reduction during the intervention will be related to longer latency to relapse. PTSD symptom change scores will be used to evaluate the degree of PTSD symptom reduction. We will fit Cox proportional hazard regression models to the data to evaluate effects of PTSD symptom reduction on the time to relapse.

Hypothesis 5. Exploratory research question: Will use of automated text messaging as an adjunct to smoking cessation be feasible, and will it impact quit rates and symptom severity? This will be evaluated by examining proportion of participants choosing to utilize text messaging, retention rates, and usage rates.

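### Two conflicting triggers for the session 15 Timeline Followback can leave some relapses after session 14 undated for Hypothesis 4, and that hypothesis's lapse outcome has no model

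*Combined protocol and SAP*

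**What the plan says.** **When TLFB is given.** Table 2, session 15, lists it after abstinence verification: "If Not Abstinent, Timeline Follow Back". The Relapse section says of the follow-up session that "if a participant reports an inability to attain or maintain abstinence, we will utilize the Timeline Followback (TLFB) method". It describes an interview of about 15 minutes that looks back over the time since participation, and states its purpose: "This information will be used to evaluate smoking rates post-quit and relapse incidence among the sample".

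**How relapse is tracked earlier.** Assessments After Screening states: "Abstinence and relapse will be monitored by ED entries and at visits 7-14". Past-week smoking is also asked before each session. The Intervention Protocol adds monthly therapist calls, with no data capture stated.

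**Re-quitting is expected.** Repeat quit attempts are encouraged until the 6-month visit. The Nicotine Replacement Therapy section says of a participant who has not stayed abstinent that "he/she may be allowed to reinitiate NRT during the follow-up period in order to make a renewed quit attempt".

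**Hypothesis 4.** In Objectives, greater symptom reduction "will result in longer duration to smoking lapse and relapse". The analysis section repeats that hypothesis in its list, then restates it for relapse alone and specifies: "We will fit Cox proportional hazard regression models to the data to evaluate effects of PTSD symptom reduction on the time to relapse". Relapse is defined, as five or more cigarettes daily on three days in a row. Lapse has no analysis definition, although in the monitored weeks "participants will record any smoking lapses on the electronic diary (ED), immediately after smoking".

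**The concern.** Time to relapse is the outcome of Hypothesis 4. Read literally, Table 2 makes collection of the relapse history depend on smoking status at month 6. Someone who relapses in month 3 and is abstinent at month 6 would not be interviewed, and the plan names no other source for that date. An outcome collected selectively in this way biases a Cox model if the selection is related to the covariate. If people with greater PTSD improvement are more likely to re-quit, their relapses are more often missing, and improvement appears to delay relapse even when it does not.

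The Relapse section has a different gap. Its trigger is what the participant reports, so a person who claims abstinence but fails biochemical verification is not interviewed.

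The lapse half of the hypothesis, as it stands, would go unanswered.

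**Working it through.** The plan gives no event count, power or effect size for Hypothesis 4, so there is no stated figure to reproduce.

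**1. Timeline.** The quit date is at session 7. The nicotine replacement schedule places steps at 2, 4 and 6 weeks after quitting, and Table 2 places them at sessions 9, 11 and 13. Visits are therefore inferred to be weekly, and session 14 falls at 14 − 7 = week 7. Taking 6 months as 26 weeks:

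- Interval between session 14 and session 15: 26 − 7 = 19 weeks, and 19/26 = 73% of follow-up.
- Diary coverage after quitting: the first week of the quit attempt and the first week after treatment, so 2/26 = 8%.
- Look-back at session 15 without TLFB: the past-week questions, and point-prevalence abstinence over 7 and 30 days. Thirty days is 4.3 weeks, which leaves about 14.7 of the 19 weeks out of reach. Point prevalence also gives a yes or no, not a date.

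**2. Who is interviewed at session 15 under each text.**

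| Participant | Table 2 | Relapse section |
|---|---|---|
| Smoking at month 6 and says so | Yes | Yes |
| Relapsed after session 14, re-quit, abstinent at month 6 | No | Possibly (did not maintain abstinence) |
| Claims abstinence, fails carbon monoxide at the visit | Possibly (verification is listed first) | No |
| Claims abstinence, fails cotinine | Unlikely (assayed at an outside laboratory, so the result would ordinarily come later) | No |

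Neither text covers everyone, and each misses people whom the other may reach.

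**3. Share of relapses left undated under Table 2.** This is the share of relapses after week 7 times the share of those who are abstinent again at month 6. Neither is in the documents, so both are assumed.

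Assume 75% relapse by week 26. The share of relapses after week 7 is (S(7) − 0.25)/0.75, with S(7) = 0.25^((7/26)^k) and k the Weibull shape:

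- k = 1 (constant hazard): S(7) = 0.689, late share 58%.
- k = 0.5: S(7) = 0.487, late share 32%.
- k = 0.3: S(7) = 0.393, late share 19%.

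Assume 20% or 30% re-quit at average improvement, with odds doubling per SD. Averaged over a normal distribution, that is 22% or 32%. The undated share then runs from 0.19 × 0.22 = 4% to 0.58 × 0.32 = 19%. A looser grid, with 10–40% late and 10–30% re-quitting, gives 0.10 × 0.10 = 1% to 0.40 × 0.30 = 12%.

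**4. Effect on the Cox estimate.** Simulation with 2,000 runs per setting and a true hazard ratio of 1.00 per SD. Undated relapses are treated as censored at week 26, which is an assumption. Error is two-sided at a nominal 5%.

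| Relapse pattern | Undated | Estimated HR | Error at n = 25–35 |
|---|---|---|---|
| Constant hazard | 13–19% | about 0.87–0.91 | 7–9% |
| Front-loaded (k = 0.5 or 0.3) | 4–10% | about 0.94–0.98 | 5–7% |
| Any, re-quitting unrelated to symptoms | 4–18% | about 1.00 | about 5% |

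The n of 25–35 assumes 50–70 enrolled and split equally, because Objectives words Hypothesis 4 for the CPT-C arm. Pooling both arms (n = 70) with constant hazard gives 11–15%, but that is not the population Objectives describes.

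**5. Lapse.** Objectives names two outcomes and the analysis paragraph models one. No arithmetic is needed.

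**The case against.** The strongest reply is that the Relapse section already solves the problem. A person who relapsed in month 3 did not maintain abstinence, and on that text would be interviewed about the whole period. This largely stands as a reading of that section. It does not remove the conflict with Table 2, which is the schedule staff would follow at the visit, and it leaves out those who deny smoking.

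A reader might infer that everyone who relapsed and re-quit lacks a relapse date. The documents do not support that: diary entries and visits 7–14 track all participants whatever their month 6 status, so only relapses after about week 7 are at risk. Nor is follow-up wholly blind. Therapists call monthly, and dosing of restarted nicotine replacement takes account of recent smoking. Neither is specified as a record of relapse dates, however.

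A reader might also infer that the undated cases will be analysed as never having relapsed. The plan states no censoring rule, so that is the simulation's assumption and not the plan's.

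Finally, the larger bias figures come from a constant hazard, which puts 58% of relapses after week 7. With earlier relapse the effect on error is small. That objection stands and is why a range is given.

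**Conclusion.** The point holds in limited form. The two TLFB triggers conflict, and under Table 2 a relapse after session 14 followed by a re-quit before month 6 has no stated source for its date. The resulting bias in Hypothesis 4 is possible, not shown. It would favour the hypothesis if improvement makes re-quitting more likely, run the other way if it makes it less likely, and vanish if the two are unrelated. Its size is unknown: the 4–19% undated and the hazard ratio of about 0.87–0.98 rest wholly on the assumed relapse, re-quit and censoring inputs, with the upper end needing a constant hazard.

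The lapse mismatch is plain on the text and depends on no assumption. Both points are worth correcting because the remedy is cheap.

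**What to change.** - Give TLFB to every participant who attends session 15, regardless of reported or verified abstinence, and make Table 2 and the Relapse section say the same.
- In the Hypothesis 4 analysis, date first relapse by the plan's own definition. Name the data sources (diary, visits 7–14, TLFB), the time origin and the censoring rule.
- Either define lapse and add a Cox model for time to first lapse from diary entries and visit reports, noting that the diary covers only two post-quit weeks, or remove lapse from Hypothesis 4.

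The cost is about 15 minutes per abstinent attendee. If 20–30% of 50–70 are abstinent (assumed), that is 10–21 people, or 2.5 to 5.25 staff hours in all, plus one model if lapse is kept. One limit remains: TLFB is self-report and will not reliably date relapse in people who deny smoking, so the report should count those who claimed abstinence but failed verification.
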